4.4.4 Additional Guidance

- Due to the requirement for multiple supportive care medications concurrent with dinutuximab administration, the number of lumens available for venous access should be carefully considered. Many centers use 2 central lumens routinely; institutional standards should be followed.
- Capillary leak syndrome is an expected side effect of dinutuximab therapy. Complications of capillary leak syndrome can be mitigated if euolemia is maintained. Close monitoring of heart rate and urine output is required, and fluids should be adjusted to compensate for third space losses. Use of furosemide or other diuretics is indicated in cases of pulmonary capillary leak but is not required routinely.
- Corticosteroid therapy should be used only for life-threatening conditions (i.e. treatment of increased intracranial pressure in patients with CNS metastases, symptomatic bronchospasm, stridor unresponsive to other measures or life-threatening allergic reactions). Corticosteroids will impair the immune response that is a critical part of the protocol therapy. **The use of steroids at any time during immunotherapy requires clear justification and documentation.**
- The use of intravenous immunoglobulin (IVIG) during Post-Consolidation therapy is discouraged. If necessary, its use should be limited to the first 100 days post-ASCT because IVIG may interfere with antibody (dinutuximab) dependent cellular cytotoxicity. IVIG should not be given within 2 weeks of starting dinutuximab treatment and 1 week after completing dinutuximab therapy.
- Cytokines or growth factors (G-CSF, Interferon, etc.) not included in the Treatment Plan are prohibited during immunotherapy.

Following completion of this cycle, Cycle 2 starts on Day 29 or when peripheral counts recover with ANC \geq 750/ μ L and platelets \geq 50,000/ μ L (whichever occurs later). Please refer to [Section 4.5.1](#) for additional criteria to start next cycle.

4.4.5 Therapy Delivery Map – Cycle 1

Cycle 1 is 4 weeks (28 days) in length.	_____ Patient COG ID number	_____ DOB
---	--------------------------------	--------------

Start Cycle 1 once criteria in [Section 4.4.1](#) have been met.
This TDM is on three (3) pages in length.

DRUG	ROUTE	DOSAGE	DAYS	IMPORTANT NOTES
Temozolomide (TEMO)	PO (preferred) or via enteral tube	BSA \geq 0.6 m ² : 100 mg/m ² /dose BSA < 0.6 m ² : See Dosing Table in 4.4.7 . See Dosing Nomogram for Full Dosing in Appendix VIII Dosing Nomogram for Reduced Dosing is in Appendix IX	1 - 5	Maximum dose = 200 mg See treatment details in Section 4.4.7 for dose rounding instructions. For patients unable to tolerate enteral TEMO, IV TEMO may be substituted for enteral TEMO at the same dose (Section 5.3). Administer enteral doses at least 1 hour prior to IRIN administration.
Irinotecan (IRIN)	IV over 90 minutes	BSA \geq 0.6 m ² : 50 mg/m ² /dose BSA < 0.6 m ² : See Dosing Table in 4.4.7	1 - 5	Administer IRIN at least 1 hour after the completion of enteral TEMO, see Section 4.4.7 . IRIN may be administered immediately after the completion of IV TEMO.
Dinutuximab (DIN)	IV over 10 hours*	17.5 mg/m ² /dose	2 - 5	*Infusion duration may be extended up to 20 hours if needed. Infusions should not extend beyond 20 hours, even if the full dose has not been administered. Start immediately after completion of NS bolus and IRIN infusion. See Section 4.4.7 for detailed DIN administration guidelines, and Section 4.4.3 for premedications and monitoring during the infusion.
Sargramostim (GM-CSF)	SubQ (preferred) or IV over 2 hours	250 micrograms/m ² /dose	6 - 12	See Section 4.4.7 for GM-CSF administration guidelines.
ISOTretinoin (ISOT)	PO	BSA \geq 0.6 m ² : 80 mg/m ² /dose BID BSA < 0.6 m ² : See Dosing Table in 4.4.7	8 - 21	BID dosing. See additional starting criteria for ISOT in Section 4.4.7 . Round doses to nearest 10 mg to accommodate capsule strength.

Continue to the next page for the therapy log.

Cycle 1 is 4 weeks (28 days) in length.	
 _____ Patient COG ID number _____ DOB 

---	---

Ht _____ cm Wt _____ kg BSA _____ m²

Date Due	Date Given	Day	TEMO _____ mg	IRIN _____ mg	DIN _____ mg	GM-CSF _____ micrograms	ISOT _____ mg _____ mg	Studies	
Enter calculated dose above and actual dose administered below									
		Prior to start						a – m	
		1	_____ mg	_____ mg					
		2	_____ mg	_____ mg	_____ mg			d, e	
		3	_____ mg	_____ mg	_____ mg			e	
		4	_____ mg	_____ mg	_____ mg			e	
		5	_____ mg	_____ mg	_____ mg			e	
		6				_____ mcg		d, e, f*, g*, m*	
		7				_____ mcg			
		8				_____ mcg	_____ mg _____ mg		
		9				_____ mcg	_____ mg _____ mg		
		10				_____ mcg	_____ mg _____ mg		
		11				_____ mcg	_____ mg _____ mg	d	
		12				_____ mcg	_____ mg _____ mg		
		13					_____ mg _____ mg		
		14					_____ mg _____ mg		
		15					_____ mg _____ mg	d, e, f	
		16					_____ mg _____ mg		
		17					_____ mg _____ mg		
		18					_____ mg _____ mg		
		19					_____ mg _____ mg		
		20					_____ mg _____ mg		
		21					_____ mg _____ mg	d, e, f	
		29	Begin Cycle 2 on Day 29 or when starting criteria are met, whichever occurs later (see Section 4.5.1).						

See [Section 5.0](#) for Dose Modifications for Toxicities and the COG Member website for Supportive Care Guidelines.

4.4.6 Required Observations – Cycle 1

All baseline studies must be performed prior to starting protocol therapy unless otherwise indicated below.

- | |
|--|
| 
 a. History, physical exam with vital signs b. Height, weight, BSA c. Performance status d. CBC with differential and platelets (patients who experience Grade 4 neutropenia or thrombocytopenia should have CBCs checked at least twice per week until recovery to Grade 3) e. Electrolytes, BUN, creatinine, calcium, magnesium, phosphorus f. ALT, AST, total bilirubin, albumin* g. Triglycerides* h. Pregnancy test (obtain for females of childbearing potential) i. GFR or Creatinine Clearance (only required for patients with TA-TMA) j. ECHO or MUGA k. Tumor Imaging Evaluation (Cross sectional tumor imaging [MRI or CT]; and ¹²³I-MIBG or alternatively FDG-PET scan for patients with MIBG non-avid disease at diagnosis) l. Bilateral bone marrow aspirates and biopsies m. Specimens for correlative studies. Post-dinutuximab specimen should be collected at a single time point between Day 5 (post-dinutuximab) and Day 8 (pre-ISOtretinoin). See Section 14.0 and Appendix X for details.* 
*Observations may be obtained between Days 5-8 (pre-ISOtretinoin)
 |
|--|

This listing only includes evaluations necessary to answer the study aims. OBTAIN OTHER STUDIES AS REQUIRED FOR GOOD CLINICAL CARE.

Comments

4.4.7 Treatment Details – Cycle 1

Drug doses should be calculated based on the height and weight obtained within 1 week prior to beginning Cycle 1.

Suggested administration schedule for chemotherapy (Days 1-5; temozolomide and irinotecan) and dinutuximab (Days 2-5):

- At hour 0: patient should receive oral temozolomide.
- At hour 1: start IV irinotecan over 90 minutes. On days the patient is receiving dinutuximab infusion (Days 2-5 of each cycle), start IVF bolus of normal saline (10-20 mL/kg) over 60-90 minutes.
- At hour 2.5: on days patient is receiving dinutuximab infusion (Days 2-5), start dinutuximab infusion.
- Note: Irinotecan must be administered at least 1 hour AFTER enteral temozolomide.

Temozolomide: PO daily (NG or G-tube administration is allowed)

Days: 1-5

Dose: For BSA ≥ 0.6 m², the dose for temozolomide is 100 mg/m²/dose

MAXIMUM dose = 200 mg

For patients receiving capsule formulation, see dosing nomogram in [Appendix VIII](#) and reduced dosing nomogram in [Appendix IX](#) (if dose modification is required).

For patients receiving oral liquid formulation, round according to institutional standard.

For BSA < 0.6 m², please see the table below. The dose of temozolomide in the table is expressed as final dose in **mg** to be administered regardless of formulation used.

TEMOZOLOMIDE Dosing If BSA < 0.6 m²	
BSA (m ²)	Dose
0.25-0.29	15 mg
0.30-0.34	20 mg
0.35-0.39	30 mg
0.40-0.44	35 mg
0.45-0.49	40 mg
0.50-0.54	50 mg
0.55-0.59	55 mg

Note: For patients unable to tolerate enteral temozolomide, IV temozolomide may be administered. Please refer to [Section 5.3](#) for guidance on IV temozolomide administration.

Sequencing: Enteral temozolomide must be administered at least 1 hour PRIOR to irinotecan.

Absorption is affected by food and therefore, consistency of administration with respect to food is suggested. Preferably, administer on an empty stomach (at least 1 hour before or 2 hours after food) to decrease nausea and vomiting and improve absorption. The whole dose, even if comprised of several capsule sizes, should be taken at one time at approximately the same time each day. Antiemetics are recommended 30-60 minutes prior to each dose to prevent nausea and vomiting. When using temozolomide capsules, dose according to Temozolomide Dosing Nomogram in [Appendix VIII](#). For ease of swallowing, the capsule content may be mixed with applesauce or apple juice. An oral suspension may also be compounded by a pharmacist. If emesis occurs within 20 minutes of taking a dose of temozolomide, the dose should be repeated once. If emesis occurs after 20 minutes, the dose should not be repeated.

Administration of enteral temozolomide should be documented; missed doses should be noted on therapy delivery map and/or in accordance with institutional policy/procedures.

Special precautions: Temozolomide capsules are available in 6 different strengths. Daily doses are usually comprised of multiple capsules of different strengths. To prevent errors, each strength of temozolomide capsules must be dispensed in a separate bottle and the total number of each strength of capsules needed for the full course must be dispensed at one time. See hyperlink to the drug monograph provided in [Section 6.0](#) for additional details and examples.

Irinotecan: IV over 90 minutes daily

Days: 1-5

Dose: For BSA $\geq 0.6 \text{ m}^2$, the dose of irinotecan is 50 mg/m²/dose.

For BSA $< 0.6 \text{ m}^2$, please see the table below. The dose of irinotecan in the table is expressed as final dose in **mg** to be administered.

IRINOTECAN Dosing If BSA < 0.6 m²	
BSA (m ²)	Dose
0.25-0.29	8 mg
0.3-0.34	12 mg
0.35-0.39	15 mg
0.4-0.44	18 mg
0.45-0.49	22 mg
0.5-0.54	24 mg
0.55-0.59	28 mg

Note: Irinotecan should be administered at least 1 hour after enteral temozolomide has been given.

Higher incidence of cholinergic symptoms has been reported with more rapid infusion rates.

See the Parenteral Chemotherapy Administration Guidelines (CAG) for special precautions, suggestions for patient monitoring, and hydration on the COG website at:

https://www.cogmembers.org/_files/disc/Pharmacy/ChemoAdminGuidelines.pdf

Dinutuximab: IV over 10 hours* daily

Days: 2-5

Dose: 17.5 mg/m²/dose

Note: Due to the increased risk of capillary leak and respiratory compromise with dinutuximab administration, patients should not have dyspnea at rest or an oxygen requirement when starting the first dose of dinutuximab. **Before starting dinutuximab**, please obtain a copy of management recommendations for anaphylaxis and hypotension available in [Appendix XI](#). It is recommended that these be available on the inpatient unit to facilitate treatment decisions should these symptoms occur.

Refer to [Section 4.4.3](#) for premedication and supportive care for the prevention of anticipated toxicities associated with dinutuximab, and for monitoring during the dinutuximab infusion. Additional information can be found in [Appendix XI](#).

Prior to dinutuximab administration (morning start recommended), administer IV bolus of normal saline (10-20 mL/kg) over 60-90 minutes. Bolus should be given concurrently with irinotecan infusion. On Day 2-5, start dinutuximab immediately following the completion of normal saline bolus and irinotecan infusion. Dinutuximab dose should start at 0.88 mg/m²/hour x 0.5 hour, then gradually increase to 1.75 mg/m²/hour for the remainder of the dose, if tolerated.

*The infusion duration may be extended up to 20 hours for anticipated toxicities (hypotension, tachypnea, etc.), not responding to other supportive measures, and the duration used should be recorded. **In the setting of dose reductions described in [Section 5.0](#), the infusion time must be no longer than 20 hours from initiation of dinutuximab, even if the full dose of dinutuximab antibody has not been delivered in that timeframe. Antibody administration should not be given beyond the specified schedule regardless of whether doses were modified or held per guidelines in [Section 5.0](#). The total dose given in 20 hours should be recorded.**

Sargramostim: Subcutaneous injection (preferred) or IV over 2 hours daily

Days: 6 through 12

Dose: 250 micrograms/m²/dose

Start sargramostim on Day 6 any time after the completion of Day 5 dinutuximab.

The standard route of administration is subcutaneous; in extenuating circumstances, IV administration over 2 hours is permitted. The reason for IV administration of this agent must be documented.

Sargramostim dose will be held if the total white cell count is > 50,000/ μ L. This is not a toxicity of sargramostim but rather a possible outcome related to its use. The sargramostim will be held until the total white cell count is less than 20,000/ μ L.

and then sargramostim will be resumed at 50% dose for the remainder of that cycle. Full dose sargramostim will be used for subsequent sargramostim cycles.

ISOTretinoin: PO BID

Days: 8-21 See additional starting criteria for ISOT in Section 4.4.2.

Dose: For $BSA \geq 0.6 \text{ m}^2$, the dose of ISOTretinoin is 80 mg/m²/dose BID, rounded to nearest 10 mg to accommodate capsule strength.

For $BSA < 0.6 \text{ m}^2$, please see table below. The dose of ISOTretinoin in the table is expressed as final dose in **mg** to be administered.

NOTE: dose BID. For example, if $BSA \geq 0.6 \text{ m}^2$, administer 80 mg/m²/dose BID. The total daily dose is 160 mg/m²/day.

ISOTretinoin Dosing If $BSA < 0.6 \text{ m}^2$	
BSA (m ²)	Dose
0.25-0.29	10 mg BID
0.3-0.39	20 mg BID
0.4-0.49	30 mg BID
0.5-0.59	40 mg BID

Note: Capsules can be cut and the contents squeezed into a high fat food such as ice cream or peanut butter immediately prior to administration. Capsules can be chewed (best absorbed if chewed with high fat food) or the child taught to swallow entire capsules, which is feasible and to be encouraged. Under no circumstances should ISOTretinoin be removed from the capsules for more than 1 hour prior to administering to the patient (see hyperlink to the drug monograph provided in [Section 6.0](#)). Administration via nasogastric tube or orally via syringe is discouraged.

Missed doses of isotretinoin should **NOT** be made up during the one week break between the scheduled end of isotretinoin therapy and the start of chemotherapy in the subsequent cycle to avoid delays in therapy. A duration of one week between the scheduled end of isotretinoin (day 21) and the start of chemotherapy in the subsequent cycle should be maintained (e.g., last dose of isotretinoin is on day 21 regardless of start date or missed doses and the subsequent cycle starts on day 29 if all other criteria are met).

See [Section 5.0](#) for Dose Modifications based on Toxicities.

4.5 Cycles 2-5

4.5.1 Criteria to Start Immunotherapy – Cycles 2-5

- a. ANC \geq 750/ μ L and platelet count \geq 50,000/ μ L (transfusion independent for \geq 7 days).
- b. ALT \leq 5 x ULN for age provided that the usual causes of transaminitis such as infections, tumor progression, or drug toxicity are excluded by appropriate blood and imaging studies AND the transaminitis is stable if not improving. For the purposes of this study, ULN for ALT is 45 U/L.
- c. Total bilirubin \leq 1.5 x ULN for age
- d. No evidence of serious infection, or infection under control (e.g., negative blood culture).
- e. A serum creatinine based on age/sex as described in [Section 3.2.6.2](#).
- f. Any diarrhea from preceding cycle improved to CTCAEv5.0 Grade 1 or better.
- g. All other non-hematologic toxicities not otherwise specified from the previous cycle must improve to CTCAEv5.0 Grade 2 or better
- h. To proceed to Cycle 4, patients must have no evidence of disease progression on the post-Cycle 3 evaluation. For patients with no evidence of residual soft tissue disease at the start of Post-Consolidation, cross sectional imaging (CT or MRI) may be omitted from the post-Cycle 3 evaluation; all other patients should undergo cross sectional imaging. For patients with no evidence of marrow disease at the start of Post-Consolidation therapy, bone marrow aspirates and biopsies may be omitted from the post-Cycle 3 evaluation. Patients with marrow involvement at the start of Post-Consolidation therapy should undergo bilateral bone marrow aspirates/biopsies as part of the post-Cycle 3 evaluation.

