3.2.6 Organ Function Requirements

3.2.6.1 Adequate Bone Marrow Function Defined As:

- Peripheral absolute neutrophil count (ANC) \geq 750/ μ L
- Platelet count \geq 50,000/ μ L (transfusion independent for \geq 7 days)

3.2.6.2 Adequate Renal Function Defined As:

- Creatinine clearance or radioisotope GFR \geq 70 mL/min/1.73 m², or
- A serum creatinine based on age/gender as follows:

Age	Maximum Serum Creatinine (mg/dL)	
	Male	Female
6 months to < 1 year	0.5	0.5
1 to < 2 years	0.6	0.6
2 to < 6 years	0.8	0.8
6 to < 10 years	1	1
10 to < 13 years	1.2	1.2
13 to < 16 years	1.5	1.4
\geq 16 years	1.7	1.4

The threshold creatinine values in this Table were derived from the Schwartz formula for estimating GFR²⁷ utilizing child length and stature data published by the CDC.

Note: Patients with history of transplant associated-thrombotic microangiopathy (TA-TMA) must have a creatinine clearance or radioisotope GFR at baseline to assess renal function and must meet the above criteria.

3.2.6.3 Adequate Liver Function Defined As:

- Total bilirubin \leq 1.5 x upper limit of normal (ULN) for age, and
- SGPT (ALT) \leq 5.0 x ULN for age (\leq 225 U/L)

Note: For the purpose of this study, the ULN for SGPT (ALT) has been set to the value of 45 U/L.

3.2.6.4 Adequate Cardiac Function Defined As:

- Shortening fraction of \geq 27% by echocardiogram, or

- Ejection fraction of $\geq 50\%$ by echocardiogram or radionuclide angiogram
- 3.2.6.5 Adequate Pulmonary Function Defined As:
- Absence of dyspnea at rest
 - If pulmonary function tests (PFTs) are performed, FEV₁/FVC must be $> 60\%$
- 3.2.6.6 Central Nervous System Function Defined As:
- No clinical evidence of active CNS disease at the time of study enrollment.
 - Patients with seizure disorder may be enrolled if on non-enzyme-inducing anticonvulsants and well controlled.
 - CNS toxicity from prior therapy \leq Grade 2.

Exclusion Criteria

- 3.2.7 Patients must not have had progressive disease (PD) per the revised International Neuroblastoma Risk Criteria (INRC)²⁸ since the initial diagnosis of high-risk neuroblastoma.
Exception: Progressive disease within the first 2 cycles of Induction chemotherapy consisting of cyclophosphamide and topotecan is allowed. Patients with progression subsequent to initial cyclophosphamide and topotecan cycles are excluded.

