4.3.4 CYP3A4 Active Agents

See [Appendix VII](#) for a list of CYP3A4 active agents.

Irinotecan is a substrate for CYP3A4 (major). Patients who have received drugs that are strong inducers or inhibitors of CYP3A4 within 7 days prior to study enrollment are not eligible. The use of strong inhibitors or inducers of CYP3A4 ([Appendix VII](#)) should be avoided for the duration of protocol therapy. Consult drug information references for further information.

In addition, concomitant use of BCRP inhibitors (cyclosporine, eltrombopag, gefitinib), and UGT1A1 inhibitors (diclofenac, ketoconazole, probenecid, silibinin, nilotinib, and atazanavir) should be avoided due to potential increased risk of irinotecan toxicity.

Moderate inducers or inhibitors of CYP3A4 ([Appendix VII](#)) should also be avoided during protocol therapy, if reasonable alternatives exist.

4.4 Cycle 1

4.4.1 Criteria to Start Immunotherapy – Cycle 1

Laboratory parameters must be within the range defined under eligibility ([Section 3.2.6](#)).

4.4.2 Criteria to Start ISOTretinoin – Cycle 1

- ALT < 10 x ULN for age. For the purposes of this study, ULN for ALT is 45 U/L.
- Serum triglycerides < 500 mg/dL.
- A serum creatinine based on age/gender as described in [Section 3.2.6.2](#).

Note: Observations may be obtained within 4 days prior to start of ISOTretinoin (i.e., Days 5-8 of protocol therapy).

As per [Section 5.2.8 Management of Concurrent Transplant Associated-Thrombotic Microangiopathy \(TA-TMA\)](#), ISOTretinoin may be dose-reduced or omitted per institutional practice in patients with TA-TMA.

4.4.3 Premedication and Supportive Care Recommended for the Prevention of Anticipated Toxicities Associated with Dinutuximab

Neuropathic pain, allergic reactions, and fever are commonly seen in patients receiving this antibody. Institutional guidelines for supportive care during this portion of therapy should be followed. The use of the following premedications are recommended:

- IV hydration: Administer NS 10-20 mL/kg IV over 60-90 minutes just prior to each dinutuximab infusion.
- Diphenhydramine 1 mg/kg/dose (maximum 50 mg) IV/PO 20 minutes prior to dinutuximab infusion and scheduled q6h. Hydroxyzine PO (0.5-1.0 mg/kg; max dose 50 mg) may be used instead of diphenhydramine in patients for whom there is a specific indication.
- H2 antagonist (e.g., famotidine IV dose: 0.25 mg/kg/dose every 12 hours; maximum dose: 20 mg/dose)

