5.2.10 Prolonged Non-Hematologic Toxicity

Patients who do not meet criteria to start the next treatment cycle (see [Section 4.5.1](#) or [Section 4.6.1](#)) within 28 days after the planned subsequent cycle start date (i.e. there is a ≥ 4 week delay in start of next cycle) due to any ongoing non-hematologic toxicity must be removed from protocol therapy.

5.3 **Inability to Tolerate Enteral Temozolomide**

For patients unable to tolerate PO temozolomide (i.e., due to nausea, vomiting), IV temozolomide may be administered.

Suggested administration schedule for chemotherapy (Days 1-5; IV temozolomide and irinotecan) and dinutuximab (Days 2-5):

- At hour 0: patient should receive IV temozolomide over 90 minutes.
- At hour 1.5 patient should start IV irinotecan over 90 minutes. On days patient is receiving dinutuximab infusion (Days 2-5 of each cycle), start IVF bolus of normal saline saline (10-20 mL/kg) over 60-90 minutes.
- At hour 3: on days patient is receiving dinutuximab infusion (Days 2-5 of each cycle), start dinutuximab infusion.
- Note: Irinotecan may be administered immediately after the completion of IV temozolomide.

Temozolomide: IV over 90 minutes daily

Days: 1-5

Dose for IV infusion: IV temozolomide may be substituted at the same dose for patients unable to tolerate enteral dosage forms. The line must be flushed before and after administration.

Sequencing: IV temozolomide may be administered immediately prior to irinotecan.

Special Precautions: IV temozolomide contains polysorbate 80, which may increase the risk of infusion or allergic reactions. If reaction occurs, premedication with diphenhydramine 1 mg/kg (maximum dose 50 mg) and hydrocortisone 2 mg/kg (maximum dose 200 mg) may be considered. Re-challenging with enteral temozolomide is also an acceptable alternative as it does not contain polysorbate 80. May be administered through the same IV line as NS. Do not administer other medications through the same IV line.

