Patients who have dose modifications but remain on therapy and are able to complete the 5 cycles without PD within 30 weeks will not count against feasibility. Patients who meet off protocol criteria due to toxicity (i.e., require greater than one dose modification for irinotecan or temozolomide, or meet off protocol criteria for dinutuximab per [Section 5.0](#)) or other criteria for removal from protocol therapy (see [Section 8.1](#)) before completion of 5 cycles will count against feasibility. Any eligible patient with prior tandem ASCT who receives at least one dose of protocol therapy will be considered evaluable for the primary endpoint.

Note: Discontinuation of isotretinoin will not count against the feasibility endpoint on this study.

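### Section 4.5.1(e) drops the measured clearance/GFR route that entry and Cycle 1 accept, so a patient who entered by it can become a feasibility failure with unchanged renal function

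*Combined protocol and SAP*

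**What the plan says.** **Entry.** Section 3.2.6.2 gives two alternatives joined by an or. One is "Creatinine clearance or radioisotope GFR" of at least 70 mL/min/1.73 m². The other is "A serum creatinine based on age/gender as follows", followed by a table of maxima.

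**Cycle 1.** Section 4.4.1 points to Section 3.2.6 as a whole: "Laboratory parameters must be within the range defined under eligibility". Either route therefore serves.

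**Cycles 2-5.** Section 4.5.1(e) reads "A serum creatinine based on age/sex as described in" Section 3.2.6.2. It does not mention clearance or GFR.

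**Isotretinoin.** The start criteria in Sections 4.4.2, 4.5.2 and 4.6.1 use nearly the same words: "A serum creatinine based on age/gender as described in" Section 3.2.6.2.

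**Scheduled tests.** Section 4.4.6 (Cycle 1) lists GFR or clearance, required only in TA-TMA. Section 4.5.6 (Cycles 2-5) lists serum creatinine and no clearance or GFR.

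**Removal and counting.** Sections 5.1.3 and 5.2.10 both remove a patient who does not meet the start criteria "within 28 days after the planned subsequent cycle start date". The body of 5.1.3 names no cause, but its heading concerns platelets and neutrophils. Section 5.2.10 applies only to ongoing non-hematologic toxicity. Under Section 9.3.1, any eligible patient given one dose is evaluable, and removal under Section 8.1 "before completion of 5 cycles will count against feasibility".

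**The concern.** The primary endpoint is meant to show whether chemo-immunotherapy can be delivered soon after transplant. A patient whose creatinine is above the table but whose measured clearance qualifies is fit to start by the protocol's own standard. If the same kidney function then blocks Cycle 2, the resulting non-completion comes from two criteria that do not match and says nothing about tolerability. It would lower the completion rate, add to the interim non-completion count, and interrupt treatment for a patient the protocol had accepted.

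**Working it through.** **1. Is the mismatch real?** Laboratory start criteria, entry against Cycles 2-5:

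| Criterion | Section 3.2.6 | Section 4.5.1 |
|---|---|---|
| ANC | ≥ 750/µL | same limit |
| Platelets | ≥ 50,000/µL | same limit |
| ALT | ≤ 5 x ULN | same limit, with added conditions |
| Bilirubin | ≤ 1.5 x ULN | same limit |
| Renal | clearance/GFR ≥ 70, or table | table only |

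Only the renal line loses an alternative, and no reason is given.

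**2. Does it reach the endpoint?** Section 9.3.1 takes about 4 weeks per cycle.

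- Primary endpoint: 5 x 4 = 20 weeks of treatment in a 30-week window. Four cycles remain after Cycle 1, so Cycle 2 must start by week 30 - 16 = 14.
- Monitoring rule (Section 9.3.3.1): 3 x 4 = 12 weeks in an 18-week window. Cycle 2 must start by week 18 - 8 = 10.

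A patient whose creatinine stays above the table past those points fails both counts without any formal removal. If Section 5.1.3 is read by its body text, removal comes sooner, after a 4-week delay.

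**3. The plan's own figures.** For x completers of n = 40, with p = x/n and z = 1.96, the Wilson limits are

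[p + z²/2n ± z·√(p(1-p)/n + z²/4n²)] / (1 + z²/n).

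- 24/40: 44.6% to 73.7%, which excludes 75%.
- 25/40: 47.0% to 75.8%, which contains 75%.
- The interval contains 75% for x = 25 to 35.
- P(25 ≤ X ≤ 35) is 0.0769 at a true 50% and 0.4402 at a true 60%. Both match Section 9.3.1.

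At least 25 completers are therefore needed, and 40 - 25 = 15 non-completions are tolerated.

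**4. Size.** The documents do not give the number k of treated patients who qualify only by measurement, so k is an assumption. Treat those k as certain failures and let the other 40 - k complete independently with probability p, setting the interim rules aside:

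P(X ≥ 25) = Σ from x = 25 to 40-k of C(40-k, x)·p^x·(1-p)^(40-k-x).

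| k | p = 75% (target) | p = 80.6% (historical, 87/108) |
|---|---|---|
| 0 | 0.974 | 0.998 |
| 1 | 0.956 | 0.996 |
| 2 | 0.929 | 0.991 |
| 3 | 0.889 | 0.982 |
| 4 | 0.833 | 0.966 |
| 6 | 0.664 | 0.893 |

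Taking the rule literally, with 36 or more completers also falling outside it, gives 0.958, 0.950 and 0.927 at 75% for k = 0, 1 and 2.

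Each such patient lowers the observed rate by at most 1/40 = 2.5 points. At the 75% target the expected loss is 0.75 x 2.5 = 1.9 points, because some would not have completed anyway. Each is also one of the 6 of 10 or 9 of 20 non-completions that trigger Table 3.

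**The case against.** The best defence is that the reference to Section 3.2.6.2 brings in both routes, or that a routine blood test was chosen on purpose for re-treatment. Neither is excluded. But 4.5.1(e) repeats the opening of the second alternative only, 4.4.1 shows how the protocol refers to eligibility as a whole, and no clearance test is scheduled in Cycles 2-5. If sites can read it either way, like patients will be handled differently. If the choice is deliberate, entry still admits patients whom the next cycle turns away.

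The group is also likely to be small. Section 3.2.6.2 says the table was derived from a GFR-estimating formula, so disagreement between the two routes should be uncommon. That stands.

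A reader might infer more than the documents support:

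- **That blocked isotretinoin courses create feasibility failures.** Section 9.3.1 excludes isotretinoin discontinuation from the endpoint, Section 5.0 lets patients continue without it, and Cycle 6 follows the five counted cycles. Section 5.2.7 also uses clearance/GFR when creatinine exceeds twice baseline, though to set the dose and not as another way to meet the start criterion.
- **That removal is mandatory.** Section 5.2.10 needs an ongoing toxicity, which unchanged function is not, and 5.1.3 sits under a hematologic heading. The endpoint is missed without it.
- **That the pre-start re-check in Section 3.2 has the same effect.** It is judged against the eligibility limits, and a patient who never starts is inevaluable under Section 9.6.
- **That patients with a TA-TMA history are the likeliest to be caught.** Section 3.2.6.2 says they "must have a creatinine clearance or radioisotope GFR at baseline to assess renal function and must meet the above criteria". It does not say that their creatinine exceeds the table.

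**Conclusion.** The point holds in a narrow form. As written, 4.5.1(e) does not recognise a renal route by which 3.2.6.2 and 4.4.1 admit and start patients, and a patient who relies on that route fails the primary endpoint and the 18-week count for a reason unrelated to deliverability.

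The likely effect on the trial's conclusion is modest. At a true 75%, one or two such patients cost about 2 to 4.5 percentage points of the chance of reaching 25 completers; at 80.6% they cost less than 1. The effect becomes material at about four or more. That one patient separates 24/40 from 25/40 is true of any failure from any cause, and is not evidence of a large effect.

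These figures assume that creatinine stays above the table, that 4.5.1(e) is applied literally, and that k lies in the range shown.

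**What to change.** Reconcile Sections 3.2.6.2, 4.4.1 and 4.5.1(e) so that no patient can be enrolled by a renal route that the next cycle does not recognise. The study committee decides which renal criterion applies; this review takes no position on that.

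For consistency, in the same amendment:

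- align the isotretinoin start criteria in 4.4.2, 4.5.2 and 4.6.1 with each other and with 5.2.7;
- make the heading and body of 5.1.3 agree, and state how 5.1.3 and 5.2.10 treat a delay that is neither hematologic nor due to an ongoing toxicity.

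The cost is a wording amendment in these places. If both routes are kept, the few patients concerned would also need a repeat clearance/GFR. Sample size, decision rule and monitoring boundaries do not change.
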